1.2.7 Overview of Other Experience in Clinical Trials and Post-marketing Surveillance

NTZ has been marketed in the United States since 2003 and in Latin America since 1996. It is estimated that more than 250 million patients have been exposed to NTZ post-marketing worldwide. No drug-related serious adverse events have been reported during post-marketing experience with NTZ.

Phase 2 and 3 clinical studies have been conducted in approximately 5,600 subjects to evaluate the safety and efficacy of NTZ in treating parasitic, bacterial and viral infections. During these studies, no drug-related serious adverse events have been observed. The side effects have been usually of a mild transient nature, and less than 1% of subjects have discontinued therapy because of an adverse event. The most common adverse events reported in clinical trials include abdominal pain, chromaturia, diarrhea, dizziness, headache, nausea and vomiting and did not differ significantly from those of placebo except for chromaturia which was reported by 4 to 5% of subjects and is attributed to urinary excretion of NTZ metabolites. Clinical chemistry and hematology obtained before and after treatment have not revealed any abnormalities attributable to the test drug.¹⁵

1.3 Rationale for the Study

There is an important need for new treatments of influenza that may offer novel mechanisms of action, improved efficacy and safety profiles or reduced risks of resistance. There is also an important need for improvement in the methodology used to evaluate the effectiveness of influenza antiviral drugs. Notably, the patient-reported outcomes instruments used for historical clinical trials have not been validated according to current FDA standards.

This study is a multicenter randomized double-blind placebo controlled trial designed to evaluate efficacy and safety of NTZ 600 mg administered orally twice daily for five days compared to a placebo in the treatment of uncomplicated influenza. The study will employ a new patient-reported outcome questionnaire, FLU-PRO[®], that has been developed and validated according to current FDA standards. All subjects will complete the questionnaire daily for 21 days using an electronic diary for accountability.

2 STUDY OBJECTIVES

The primary objective of this study is to evaluate the effect of NTZ administered orally 600 mg b.i.d. for 5 days in reducing the duration of symptoms of influenza compared to that of a placebo during 21 days of follow up based upon the FLU-PRO[®] patient-reported outcome instrument.

A key secondary efficacy objective is to evaluate the effect of NTZ compared to placebo on time to return to ability to perform all normal activities.

Another secondary efficacy objective is to evaluate the effect of NTZ compared to placebo on the proportion of subjects experiencing one or more complications of influenza including pneumonia, otitis media, bronchitis, sinusitis, worsening of pre-existing health conditions, systemic antibiotic use for infections secondary to influenza infection, hospitalization due to complications of influenza, and death.

Exploratory efficacy objectives include evaluating the effect of treatment with NTZ on the time to response for each FLU-PRO symptom, time to response for each FLU-PRO domain, time to resolution of febrile illness, time to return to usual health, and changes in viral titers from baseline to each of days 2, 3 and 7.

Other important objectives include evaluation of the safety of NTZ by analysis of adverse events and evaluation of the effect of nitazoxanide on influenza antibody response and evaluation of relationships between pharmacokinetics and clinical or virologic responses.

3 STUDY DESIGN

The study will be a multicenter, randomized, double-blind trial to evaluate the efficacy of NTZ compared to placebo in treating uncomplicated influenza. Subjects will be selected according to the inclusion and exclusion criteria listed below. The study is designed to enroll at least 600 subjects (up to 700 maximum) with laboratory-confirmed influenza. Total enrollment required to achieve this number is expected to be approximately 800 to 1200 subjects. Prior to screening for inclusion in the study, informed consent will be obtained.

Immediately after completion of informed consent, screening, and enrollment in the study, two baseline nasopharyngeal swabs will be collected for viral culture and RT-PCR. A blood sample will be collected for laboratory safety tests and anti-influenza antibodies, and a urine sample will be collected for laboratory safety tests. Subjects will receive instruction on completion of their electronic diaries, concomitant medications and attending follow-up visits.

Then subjects will be randomized 1:1 to one of the following groups:

- Group 1 (NTZ): Two NTZ 300 mg tablets b.i.d. for 5 days
- Group 2 (Placebo): Two placebo tablets b.i.d. for 5 days

The medication will be taken twice daily with food (preferably a high-fat meal, but at minimum a cereal bar). The first dose will be taken with food in the physician's office under the observation of the Principal Investigator or a member of the Investigator's staff. The second dose will be taken by the subject as close as possible to 12 hours after the first dose.

A nurse or other study personnel will visit each subject (or the subject will return to the clinic) on study days 2 and 3 to collect two nasopharyngeal swabs, to review patient diaries, and to review symptoms and screen for influenza-related complications including sinusitis, otitis, bronchitis, pneumonia and central nervous system disease. Subjects will be referred for immediate care as needed based on the screening. A blood sample for pharmacokinetics will also be collected on study day 3. These day 2 and 3 visits will occur at approximately

the same time of day that the subject took his/her first dose of study medication (roughly 24 and 48 hours post-first dose). On day 3, the blood sample for pharmacokinetics will be collected before the dose. The nasopharyngeal swabs will be used to evaluate quantitative changes in viral shedding. The blood samples will be used to evaluate relationships between pharmacokinetics and virologic or clinical response. Study sites or subjects may opt out of the day 2 and day 3 visits due to site staffing, patient availability or other practical considerations or preferences; nevertheless, at least 75% of subjects enrolled in the trial are expected to complete the day 2 and day 3 visits and related procedures (for viral kinetics and pharmacokinetics).

A study physician, nurse or other site personnel will make daily telephone calls to subjects for the first five days of dosing to review symptoms and screen for influenza-related complications including sinusitis, otitis, bronchitis, pneumonia and central nervous system disease. Subjects will be referred for immediate care as needed based on the screening. [Note: In lieu of a telephone call, this information may be obtained during the day 2 or 3 office or home visits (see the preceding paragraph).] The study sites and subjects will be blinded from virology laboratory data until after study day 22 or, if earlier, until the subject is discontinued from the study. During the study period, each subject will be presumed to have influenza infection, and any worsening of symptoms or complications will be presumed to be influenza-related.

Subjects will return to the clinic on days 7 and 22 for post-treatment follow-up, including two nasopharyngeal swabs, drug accountability, reporting of adverse events and complications of influenza. Blood and urine samples for laboratory safety tests will be collected at day 7, and a blood sample for anti-influenza antibodies will be collected on day 22. A nurse or other study personnel will review the electronic patient diary entries daily (synchronized to a web-based data system) to ensure contemporaneous and complete recording of diary data. Subjects will maintain the electronic patient diaries until study day 22. Any visits that do not occur on the prescribed date, or within 1 day of that date in the case of the day 7 visit or within 3 days after that date in the case of the day 22 visit, will be recorded as protocol deviations.

A central laboratory will be used for laboratory safety tests, anti-influenza antibodies and virology testing. Laboratory safety tests will include hemoglobin, hematocrit, complete blood count (total and differential), platelet count, random blood sugar, total cholesterol, HDL, LDL, triglycerides, albumin, AST, ALT, GGT, alkaline phosphatase, bilirubin (total/direct), BUN, creatinine, sodium, potassium, chloride and routine urinalysis (glucose, protein and blood). Virology testing will include RT-PCR assay ePlex[®] Respiratory Pathogen Panel (GenMark, Carlsbad, CA) to identify influenza A (non-specific as to subtype); influenza A H1, H1N1 (2009) and H3 subtypes; influenza B; respiratory syncytial virus A and B (RSV); parainfluenza 1, 2, 3 and 4; human metapneumovirus (hMPV); adenovirus (A-F); human rhinovirus/enterovirus; coronavirus NL63, HKU1, 229E and OC43; *Chlamydomphila pneumoniae*; and *Mycoplasma pneumoniae* (baseline and day 7 nasopharyngeal swabs), culture (baseline and day 7 nasopharyngeal swabs), and quantitation of influenza viruses by TCID₅₀ (baseline and days 2, 3 and 7 nasopharyngeal swabs). Follow-up samples (days 2, 3, 7 and 22) collected from subjects who do not test positive for influenza A or influenza B at baseline will not be analyzed for quantitative influenza viral titer.

This study is expected to run from December 2017 through April 2019.

Rationale for important issues in the study design is described below:

- *Choice of NTZ dose and duration of treatment.* The dose of NTZ used for this clinical trial (600 mg b.i.d. for 5 days) was selected based upon results of a Phase 2b/3 dose-range finding clinical trial (Study RM08-3001) conducted in the United States during the 2010-2011 flu season. In that study, treatment with 600 mg NTZ b.i.d. for 5 days was associated with a statistically significant reduction in time from first dose to alleviation of symptoms compared to the placebo. A 300 mg NTZ dose group also experienced a reduction of time to alleviation of symptoms compared to the placebo, but the difference was not statistically significant. The 600 mg NTZ dose was well tolerated. Adverse events reported for subjects receiving the

600 mg dose were similar to those of subjects receiving the placebo, with the exception of a higher rate of diarrhea (8.1% compared to 3.3% for the placebo).

- *Choice of control groups.* According to FDA Guidance, a placebo-controlled rather than non-inferiority design should be used for trials evaluating treatment of uncomplicated influenza because the risks of receiving a placebo are low, and the efficacy of available treatment is modest, variable and cannot be predicted well enough to support an adequate inferiority margin.²⁴
- *Choice of patient population.* The population to be studied includes adults and adolescents at least 12 years of age with uncomplicated influenza. This is a population similar to those selected for studies RM08-3001, RM08-3002, and RM08-3003 of the NTZ 300 mg extended release tablets. No safety concerns have been identified from these clinical trials.

For the present study, some subjects (e.g., subjects >65 years of age, mild asthma, stage I or II COPD, diabetes mellitus if not poorly controlled, etc. – see Inclusion/Exclusion criteria in Sections 4.1 and 4.2) who are at higher risk of influenza complications according to CDC criteria will be allowed to participate if, in the judgment of the investigator, they are able to comply with protocol requirements and do not have a pre-existing illness or condition that would place them at an unreasonably increased risk. Inclusion of these patients in the study will improve recruitment efforts and will provide important data related to the effectiveness and safety of the NTZ 300 mg extended release tablets in this population. Notably, there is limited evidence to support the effectiveness of existing influenza antivirals in subjects at higher risk of influenza complications.

Data from pharmacokinetics studies in healthy volunteers 12 to 17 years of age or 18 to 65 years of age indicate that the pharmacokinetics of the major NTZ metabolites, tizoxanide and tizoxanide glucuronide, following oral administration of a NTZ 500 mg tablet are similar for these age groups. Safety data is also similar for these age groups. Therefore, the adult dose is deemed appropriate for pediatric patients down to 12 years of age. Informed consent will be required for subject participation in this study (see Protocol Section 15). A signed assent form will be required for any minors enrolled (\leq 18 years of age or as local regulations apply) as well as a signed parental/legal guardian consent by their parent/legal guardian allowing for the minor's participation.

According to FDA Guidance, antiviral drug efficacy in children cannot be extrapolated from data generated from trials in adults because: (1) prior exposure and immunity typically present in adults may affect influenza illness and response to treatment differently than in children; and (2) viral shedding may differ in pediatric and adult age groups.²⁴ Study of the efficacy and safety of the product in children is, therefore, required in order to have the product licensed for use in pediatric patients. Separate subset analyses of safety, pharmacokinetics and efficacy data for pediatric patients will be performed to evaluate the safety and efficacy of NTZ in this population.

- *Choice of Patient-Reported Outcome Instrument.* This clinical trial will use a new, recently released patient-reported outcome questionnaire, InFLUenza Patient-Reported Outcome Questionnaire (FLU-PRO[®]).

FLU-PRO was developed with the support of the U.S. Department of Health and Human Services through the National Cancer Institute and the National Institutes of Allergy and Infectious Diseases, National Institutes of Health, in response to the need for improved metrics to evaluate treatment effect in clinical trials of drugs for treatment of influenza. It was developed and validated in accordance with FDA's guidance, "Patient-Reported Outcome Measures: Use in Medical Product Development to Support Labeling Claims." It has also been validated for use on an electronic device as part of an electronic diary ("eDiary") that can time stamp diary entries to ensure timely recording, thereby mitigating risks of recall bias. We will use an electronic diary for this clinical trial.

FLU-PRO is designed to comprehensively assess the presence and severity of influenza symptoms across body systems. The questionnaire has addressed issues that limit interpretation of historical influenza studies by including extensive input from influenza-infected patients to ensure that (1) all symptoms of influenza are assessed (content validity), and (2) the questions are asked in a manner and with response options that patients understand (context validity) and that distinguish between known groups. The resulting instrument assesses 32 symptoms of influenza across six domains (nose, throat, eyes, chest/respiratory, gastrointestinal, body/systemic). Each question provides 5 response options instead of 4 used in traditional PRO instruments.^{25,26}

- *Choice of Endpoints.* The primary efficacy endpoint for this study will be Time to Symptom Response based upon the FLU-PRO[®] instrument. This is directed to the way the patient “feels” as measured by his/her symptoms. A Symptom Response definition will be developed based upon a blinded review of FLU-PRO symptom scores (pooled for all subjects without regard to treatment group assignment so as to maintain blinding) and correlation of those scores to the time at which subjects report that they have returned to their usual state of health (a “yes” or “no” question incorporated into the daily Questionnaire). The Time to Symptom Response used for evaluating the primary endpoint will be calculated based upon this response definition and programmed prior to database unblinding for the primary analysis. This anchor-based approach to defining responders ensures that the symptom response definition is valid and meaningful for the subjects participating in each given clinical trial – a point that may be particularly important in the case of an illness like influenza that is not uniform from year to year.

The key secondary endpoint will be Time to Ability to Perform All Normal Activities. This endpoint will provide important information with respect to the way a patient “functions.” Each of the previous clinical trials of NTZ in subjects with influenza have indicated improvement in this endpoint while data collection from those studies has typically not extended out long enough to fully characterize the benefit.

Another secondary endpoint will be proportions of subjects experiencing complications of influenza. We do not expect to see enough complications of influenza in this population to demonstrate differences between treatment groups, and therefore, this endpoint is lesser in priority compared to Time to Ability to Perform All Normal Activities. All other efficacy endpoints will be considered exploratory.

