5.5 Day 2 and 3 Evaluations

A study physician, nurse or other study personnel will visit each subject at home (or at the clinic or another location as agreed with the subject) on each of days 2 and 3 to (i) collect two nasopharyngeal swabs for detecting (RT-PCR) and quantifying (TCID_{50}) influenza virus, and (ii) review symptoms and screen for influenza-related complications including sinusitis, otitis, bronchitis, pneumonia, central nervous system disease and worsening of pre-existing health conditions as well as adverse events. Subjects will be referred for immediate care as needed based on the screening. All information gained from these visits will be included in the case report forms for each subject. In addition, a blood sample for pharmacokinetics will be collected on day 3. The day 2 and day 3 visits will occur at approximately the same time of day that the patient took his/her first dose of study medication (approximately 24 and 48 hours after the first dose). On day 3, the blood sample for pharmacokinetics will be collected before the first dose of that day.

Study sites or subjects may opt out of these day 2 and day 3 visits due to site staffing, patient availability or other practical considerations or preferences; nevertheless at least 75% of subjects enrolled in the trial are expected to complete the day 2 and day 3 visits and related procedures (for viral kinetics and pharmacokinetics).

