5.11 Plan for Virology Testing and Monitoring Resistance

In an effort to monitor potential resistance to tizoxanide during study RM08-3004, the following procedures will be performed:

- 1) Collection of samples:
Two nasopharyngeal swabs will be collected from each patient at Baseline (day 1) and days 2, 3, 7 and

- 22.
- 2) Testing of biological samples
 - a. Each Baseline sample will be subjected to: (1) culture to detect influenza A and B, (2) RT-PCR using the ePlex[®] Respiratory Pathogen Panel (GenMark, Carlsbad, CA) to detect influenza A (non-specific as to subtype); influenza A H1, H1N1 (2009), H3 subtypes; influenza B; respiratory syncytial virus A and B (RSV); parainfluenza 1, 2, 3 and 4; human metapneumovirus (hMPV); adenovirus (A-F); human rhinovirus/enterovirus; coronavirus NL63, HKU1, 229E and OC43; *Chlamydomphila pneumoniae*; and *Mycoplasma pneumoniae*.
 - b. If a subject's Baseline sample is negative for influenza by RT-PCR, his/her day 2 and day 3 samples will be subjected to RT-PCR using the ePlex[®] Respiratory Pathogen Panel to detect respiratory pathogens.
 - c. If the Baseline sample or the day 2 or day 3 sample is positive for influenza A or influenza B, the Baseline sample and each of the day 2 and 3 samples will be subjected to TCID₅₀ to quantify viral shedding.
 - d. Day 7 samples will be subjected to culture and RT-PCR using the ePlex[®] Respiratory Pathogen Panel. All samples positive for influenza A or influenza B will also be subjected to TCID₅₀ to quantify viral shedding.
 - e. Day 22 samples will be subjected to culture and RT-PCR using the ePlex[®] Respiratory Pathogen Panel only if the sample collected at the preceding time point (day 7) had detectable influenza virus. All samples positive for influenza A or influenza B will also be subjected to TCID₅₀ to measure viral shedding.
 - 3) Drug susceptibility testing
 - a. If any day 7 or day 22 sample is positive for influenza A or influenza B by culture, the virus will be isolated and tested for susceptibility to tizoxanide (TCID₅₀).
 - b. The Baseline isolate for subjects with virus cultured at day 7 or 22 will also be tested for susceptibility to tizoxanide, and the results will be compared to the results observed for the day 7 or 22 isolate.
 - 4) Nucleotide sequencing

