Subjects will return to the clinic on days 7 and 22 for post-treatment follow-up, including two nasopharyngeal swabs, drug accountability, reporting of adverse events and complications of influenza. Blood and urine samples for laboratory safety tests will be collected at day 7, and a blood sample for anti-influenza antibodies will be collected on day 22. A nurse or other study personnel will review the electronic patient diary entries daily (synchronized to a web-based data system) to ensure contemporaneous and complete recording of diary data. Subjects will maintain the electronic patient diaries until study day 22. Any visits that do not occur on the prescribed date, or within 1 day of that date in the case of the day 7 visit or within 3 days after in the case of the day 22 visit will be recorded as protocol deviations.

A central laboratory will be used for laboratory safety tests, anti-influenza antibodies and virology testing. Laboratory safety tests will include hemoglobin, hematocrit, complete blood count (total and differential), platelet count, random blood sugar, total cholesterol, HDL, LDL, triglycerides, albumin, AST, ALT, GGT, alkaline phosphatase, bilirubin (total/direct), BUN, creatinine, sodium, potassium, chloride and routine urinalysis (glucose, protein and blood). Virology testing will include RT-PCR assay to identify influenza A (non-specific as to subtype); influenza A H1, H3 and H1N1 (2009) subtypes; influenza B; respiratory syncytial virus A and B (RSV); parainfluenza 1, 2, 3 and 4; human metapneumovirus (hMPV); adenovirus; human rhinovirus/enterovirus; coronavirus NL63, HKU1, 229E and OC43; human bocavirus; *Chlamydomphila pneumoniae*; *Legionella pneumophila*; and *Mycoplasma pneumoniae* (baseline and day 7 nasopharyngeal swabs), culture (baseline and day 7 nasopharyngeal swabs), and quantitation of influenza viruses by TCID₅₀ (baseline and days 2, 3 and 7 nasopharyngeal swabs). Follow-up samples (days 2, 3 and 7) collected from subjects who do not test positive for influenza A or influenza B at baseline will not be analyzed for quantitative influenza viral titer.

This study is expected to run from December 2017 through April 2019.

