8. DATA DEFINITIONS AND CONVENTIONS

8.1 Analysis Populations

Three populations will be designated for the purpose of these analyses:

Table 1. Definition of Analysis Populations

Analysis Population	Definition
All Treated	All subjects who receive at least one dose of study medication
Confirmed Influenza	The subset of the All Treated population who are positive for influenza by RT-PCR or culture at any of the Baseline, Day 2 or Day 3 visits
Per Protocol	The subset of the Confirmed Influenza population with no major protocol deviations that may have an effect on the integrity of the data or the evaluation of effectiveness

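### Protocol Section 3 and SAP 7.2 bar titration of follow-up swabs that Protocol 5.11 requires, and SAP 10.5.6 can then score a culture-positive Day 7 subject as virus-negative

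*Protocol*

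**What the plan says.** The virology paragraph in Protocol Section 3 assigns swab days to each assay. RT-PCR is given baseline and Day 7, followed by "culture (baseline and day 7 nasopharyngeal swabs), and quantitation of influenza viruses by TCID₅₀ (baseline and days 2, 3 and 7 nasopharyngeal swabs". SAP 7.2 gives the same days for RT-PCR and culture: "baseline and day 7 nasopharyngeal swabs), culture (baseline and day 7 nasopharyngeal swabs". Neither list mentions RT-PCR on Days 2 and 3.

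Both paragraphs then bar titration. In Protocol Section 3 the bar covers Days 2, 3, 7 and 22 for subjects "who do not test positive for influenza A or influenza B at baseline will not be analyzed for quantitative influenza viral titer". SAP 7.2 applies it to "Follow-up samples (days 2, 3 and 7) collected from subjects who do not test positive for influenza A or influenza B at baseline".

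Protocol 5.11 sets different rules. Item 2(b) sends Day 2 and Day 3 samples for RT-PCR when the baseline RT-PCR is negative. Item 2(c) begins "If the Baseline sample or the day 2 or day 3 sample is positive for influenza A or influenza B" and then requires TCID50 on the baseline, Day 2 and Day 3 samples. Item 2(d) requires TCID50 on every influenza-positive Day 7 sample, with no condition on baseline. Protocol 5.5 agrees with 5.11: the purpose of the Day 2 and 3 visits is to "collect two nasopharyngeal swabs for detecting (RT-PCR) and quantifying" virus.

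The efficacy population in SAP Table 1 is treated subjects who are "positive for influenza by RT-PCR or culture at any of the Baseline, Day 2 or Day 3 visits". Protocol 8.4.1 uses the same three time points and the same two assays.

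**The concern.** A subject who is negative at baseline and positive on Day 2 or 3 is a full member of the Confirmed Influenza population. For that subject, one set of sections forbids titration of the follow-up swabs and another requires it. Neither document says which governs.

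SAP 10.5.5 (change in titre to Day 2 and to Day 3) and SAP 10.5.6 (detectable virus on Days 2, 3 and 7) are both run on Confirmed Influenza. Their denominators, and some of their results, therefore depend on which section the laboratory followed. A missing titre is also not always neutral, because 10.5.6 turns a missing Day 7 titre into a negative result.

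**Working it through.** **Step 1. Follow one subject through both rules.** Take a subject negative at baseline by RT-PCR and culture, RT-PCR-positive on Day 2, and culture-positive on Day 7.

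| Test or status | Protocol 3 and SAP 7.2 | Protocol 5.11(2) |
|---|---|---|
| Day 2/3 RT-PCR | not listed | required, (b) |
| In efficacy population once Day 2 is positive | yes | yes |
| Day 2/3 TCID50 | barred | required, (c) |
| Day 7 RT-PCR and culture | listed | required, (d) |
| Day 7 TCID50 | barred | required, (d) |

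The first row is an omission. The two TCID50 rows are contradictions.

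**Step 2. Carry the subject into the analyses.**

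- SAP 10.5.5 needs a Day 2 or Day 3 titre and a baseline titre. Under SAP 7.2 the subject contributes nothing; under 5.11 all three samples are titrated.
- SAP 10.5.6, Days 2 and 3: the denominator is confirmed subjects with a TCID50 result. Under SAP 7.2 the subject is absent; under 5.11 the subject is counted.
- SAP 10.5.6, Day 7: the denominator is all confirmed subjects, and no TCID50 result counts as negative. The stated reason is that samples were not titrated when traditional culture was negative. Under SAP 7.2 this subject goes untitrated for another reason, namely a negative baseline, and is scored negative with a positive Day 7 culture on file. Under 5.11 the sample is titrated and scored on its result.

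So, under SAP 7.2, the same subject is left out on Days 2 and 3 and counted as virus-free on Day 7.

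**Step 3. Culture on Days 2 and 3.** Both population definitions accept culture on those days, and Protocol 8.2 (exploratory item vi) and 8.4.1 plan to compare culture detection then. No section schedules an assay named culture on Day 2 or 3. The assay scheduled is TCID50, itself a tissue-culture assay, and SAP 10.5.6 uses it for the detection comparison. Under 5.11(2)(c), Day 2/3 TCID50 is run only after a baseline, Day 2 or Day 3 sample is already positive, so it cannot by itself add anyone to the population. The mismatch is one of naming.

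**Step 4. Size.** No figure in the plan is in dispute. The scale reproduces: 552 / (1 − 0.08) = 600 confirmed subjects. The share first positive on Day 2 or 3 is not given, so it has to be assumed:

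- 2%: 0.02 × 600 = 12
- 5%: 0.05 × 600 = 30
- 10%: 0.10 × 600 = 60

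These subjects would have Day 2/3 titres under 5.11 and none under SAP 7.2. Only those with virus still present on Day 7 would be mis-scored there. Under each assumption, the pooled Day 7 proportion could therefore be understated by at most 2, 5 or 10 percentage points.

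**The case against.** The strongest reply is that 5.11 is the dedicated virology section and Section 3 a summary. The summary states what testing includes, not what it excludes, and it is visibly incomplete: its bar refers to Day 22 titration although its list gives none, and it leaves out the conditional Day 22 RT-PCR and culture planned in Protocol 5.7 and 5.11(2)(e). For RT-PCR this reply stands. Leaving out a conditional test does not forbid it. For titration it fails, because the bar is categorical and the SAP repeats it. If the laboratory follows 5.11 in practice, the damage shrinks to a wrong description in two paragraphs, but the documents do not ensure that.

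Two stronger readings are tempting.

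A reader might infer that the primary efficacy population is itself ambiguous and that power is at risk. If late-confirmed subjects were dropped from a fixed 600, then 588, 570 or 540 would remain. With 8% incomplete (540.96, 524.4 and 496.8), power = Φ[(1.960 + 1.282) × √(n/552) − 1.960] gives about 89.4%, 88.5% or 86.8%. The documents do not support this reading. Protocol 8.4.1 and SAP Table 1 define the population alike, Protocol 5.5 and 5.11(2)(b) supply the Day 2/3 RT-PCR, and enrolment to 600 under one rule costs no power.

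A reader might also take study RM08-3001 as an upper bound. Confirmed influenza there rose from 257/624 = 41.2% to 46% (0.46 × 624 ≈ 287), about 30 more subjects, or 30/287 = 10.5% of the enlarged group. That is not a bound. The RT-PCR method changed, positives through Day 7 counted, and Day 2 to 5 swabs came from a subset at about 20% of sites. Here at least 75% of subjects are expected to complete the Day 2 and 3 visits. The yield could differ in either direction.

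**Conclusion.** The titration rules contradict each other, and one consequence is a wrong score: under SAP 7.2 with 10.5.6, a subject confirmed only on Day 2 or 3 with a culture-positive Day 7 swab is counted as having no virus. The missing Day 2/3 RT-PCR in the two summary lists is an omission that 5.11 fills. The reach is the exploratory titre and viral-detection analyses, not the primary population or its power. The number affected is unknown; 12, 30 or 60 of 600 rests on assumed shares of 2%, 5% or 10%, and fewer would be mis-scored on Day 7. The effect on the treatment comparison cannot be given a direction, since nothing indicates how late confirmation would divide between the arms. It should be corrected before unblinding.

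**What to change.** 1. In Protocol Section 3 and SAP 7.2, keep the assay and pathogen lists. Add Day 2 and Day 3 RT-PCR for subjects whose baseline RT-PCR is negative.
2. In both places replace only the final titration-bar sentence with the 5.11(2)(c)-(d) rule: TCID50 on the baseline, Day 2 and Day 3 samples of every subject positive on any of those days, and on positive Day 7 samples. State whether a positive Day 7 sample means by culture or by either assay, since 5.11(2)(d) does not say and 10.5.6 assumes culture.
3. In SAP 10.5.6, score a missing Day 7 TCID50 as negative only when the Day 7 culture was done and was negative. Otherwise treat it as missing, and define the Day 7 denominator to match.
4. Reconcile the word culture at Days 2 and 3 in Protocol 8.2 (item vi), both places in Protocol 8.4.1, and SAP Table 1 with the assay scheduled, TCID50. Change all of them together; editing only the population definitions would leave the planned culture comparison without a matching assay.

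The cost is wording, plus a few more titrations than Section 3 implies but none beyond those planned in 5.11. Samples are kept for at least two years, so gaps could be filled before unblinding. Item 3 turns some Day 7 negatives, such as subjects who missed the visit, into missing values.
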